6.6.7 Other Events Requiring Immediate Reporting

The Investigator must report a pregnancy that occurs in a subject during a clinical study to the Drug Safety Contact within 24 hours of first becoming aware of the event. Pregnancy should be reported on a Pregnancy Report Form. The Investigator should discuss the case with the Medical Monitor; the Investigator must follow any pregnant subject for 3 months after the child is born. Any AEs concerning the pregnancy of the subject during pregnancy or the child after birth must be documented and reported to the Sponsor.

Acute suicidal crisis or clinically significant suicidal behavior or ideation should be reported to the Drug Safety Contact within 24 hours of first becoming aware of the event.

6.6.8 Sponsor Responsibilities for Reporting SAEs

The Sponsor will inform Investigators and regulatory authorities of reportable events, in compliance with applicable regulatory requirements, on an expedited basis (i.e., within specific timeframes). For this reason, it is imperative that study sites submit SAE information to the Sponsor in the manner described above.

Investigators must comply with the applicable regulatory requirements related to the reporting of SAEs to the IRB. Investigators must also submit the safety information provided by the Sponsor to the IRB unless the country legal regulation requires that the Sponsor should be responsible for the safety reporting to the IRB.

It is the responsibility of the Sponsor to notify all participating investigators, in a written IND safety report, of any SADR that is both serious and unexpected. The Sponsor will also notify participating investigators if applicable of any findings that suggest a significant risk for human subjects. Such findings will typically lead to safety-related changes in the study protocol, Informed Consent, and/or Investigator's Brochure.

6.6.9 Adverse Events of Special Interest

An AESI (serious or non-serious) is one of scientific and medical concern specific to the sponsor's product or program, for which ongoing monitoring and rapid communication by the investigator to the sponsor can be appropriate. Such an event might warrant further investigation in order to characterize and understand it. Depending on the nature of the event, rapid communication by the trial sponsor to other parties (e.g., regulatory agencies, IRB, etc.) might also be warranted.

Several AEs are known to be associated with the long-term use of TPM and can be expected with treatment with SPN-538 (["National Institutes of Health-DailyMed- Trokendi XR- Prescribing Information.," 2022](#)). Consistent monitoring is required for the following AESIs:

- Metabolic acidosis (serum bicarbonate)
- Hyperammonemia
- Oligohydrosis and hyperthermia
- Clinically significant increase in alkaline phosphatase, creatinine, or eosinophils (specifically, for patients 6 to 11 years, these were noted to be abnormally increased more frequently with TPM than with placebo)
- Clinically significant decrease in total white cell count or neutrophils
- Visual changes: subjects presenting with blurry vision, ocular pain, and visual field defects must be discontinued early and closely followed to ensure a prompt resolution of ocular AEs.

- Suicidal behavior and ideation
- Serious skin reactions (TPM should be discontinued at the first sign of rash, unless rash is not drug-related)
- Negative effect on growth (weight and height)
- Cognitive and memory function impairments
- Nephrolithiasis

The Site Investigator must report all AESIs to Supernus drug safety team within 24 hours of becoming aware of the information using the SAE/AESI Report form.

6.7 Treatment-Emergent Suicidal Ideation

Prospective assessment of suicidal ideation and suicidal behavior is a mandatory part of the safety evaluations for any drugs developed for epilepsy and psychiatric indications ("[Center for Drug Evaluation and Research. Suicidal Ideation and Behavior](#)," 2012). In this study, the initial evaluation of subjects will be conducted prior to enrollment to assess lifetime suicidal ideation and to identify subjects who must not participate in the trial due to pre-existing suicidality risk. The assessment will then be repeated at each subsequent study visit (except telephone contacts) to monitor the occurrence of new suicidal and self-injurious tendencies.

6.7.1 Columbia Suicide Severity Rating Scale (C-SSRS)

Assessment of suicidal ideation and behavior will be conducted using the C-SSRS ([Appendix 10.6](#)). The C-SSRS is an FDA-recommended prospective assessment instrument that directly classifies suicidal ideation and behavior events into 11 preferred categories, including 5 levels of suicidal ideation, 5 levels of suicidal behavior, and the category of self-injurious behaviors with no suicidal intent.

The instrument has been validated and used successfully in both children and adolescent patients with various psychiatric disorders that do not involve cognitive impairment. The C-SSRS outcomes that can be used for clinical management and safety monitoring are suicidal lethality rating, suicidal ideation score, and suicidal ideation intensity rating. In this study, the Children's Baseline version ([Appendix 10.6.1](#)) will be used at Screening, and the Children's Since Last Visit version ([Appendix 10.6.2](#)) will be used at each subsequent clinic visit.

6.7.2 Suicide Risk Management Plan

The protocol procedures related to clinical care of patients with treatment-emergent suicidal ideation and behavior must be implemented to ensure proper management of the event and protection of subjects' safety. If a disclosure of suicidal ideation is revealed as part of the C-SSRS questionnaire or when a subject spontaneously expresses that he/she may be a threat to him/herself, the study team should be

prepared to quickly evaluate the event and to determine the appropriate course of action.

6.7.3 Assessment of Suicide Risk

Any indication of suicidal ideation should be evaluated as soon as possible by appropriately trained staff. The Investigator is responsible for making the final judgment regarding potential suicide risk and need for subsequent action.

6.7.4 Acute Suicidal Crisis

A person evaluated as being at high risk should be transferred to an immediate care facility. The Investigator will guide intervention as clinically indicated and follow up with the subject within 1 week and/or refer him/her to a qualified mental health professional.

6.7.5 Non-acute Suicidal Risk

The Investigator will conduct safety planning with the subject and will follow up within 1 week. Reference materials for subjects and caregivers should include lists of mental health organizations and professionals, outpatient behavioral services, local crisis, and peer support groups and Suicide/Crisis Hotlines.

6.8 Clinical Measurements

6.8.1 Laboratory

All clinical laboratory tests will be performed by a central laboratory as specified in the reference binder.

Details for collecting, handling, and shipping samples (including shipment addresses) will be detailed in a separate clinical laboratory manual. The Schedule of Events and Assessments ([Table 2](#)) shows the time points at which blood and urine samples will be collected for clinical laboratory tests.

[Table 3](#) presents the clinical laboratory tests to be performed.

Table 3 Clinical Laboratory Tests

Category	Parameters
Hematology	Red blood cell count, hemoglobin, hematocrit, platelets count, and white blood cell count with differential
Serum Chemistry	Electrolytes: Na ⁺ , K ⁺ , phosphate, chloride, bicarbonate
	Liver function tests: alkaline phosphatase, aspartate aminotransferase, alanine aminotransferase, total bilirubin, direct bilirubin, gamma-glutamyl transpeptidase
	Renal function parameters: blood urea nitrogen, creatinine
	Other: glucose, Ca ²⁺ , albumin, total protein, ammonia

Category	Parameters
Urinalysis and urine pregnancy test (FOCP only)	Complete urinalysis with microscopic examination, human chorionic gonadotropin
Urine Drug Screen	Cocaine, amphetamines, barbiturates, benzodiazepines, cannabinoids, opioids, phencyclidine, propoxyphene, methadone and alcohol
Serum Pregnancy Test (FOCP only)	Human chorionic gonadotropin

6.8.2 Vital Signs

Vital signs' measurements (e.g, BP, pulse rate, temperature, and RR) will be obtained at each visit. BP and pulse rate will be measured after the subject has been sitting for 5 minutes. Route of temperature may be oral or temporal, per clinical practice, but should remain consistent throughout the subject's participation. Vital signs may be taken at any other time, as deemed necessary by the Investigator.

6.8.3 Medical and Psychiatric History

Medical and psychiatric history will be collected at Screening as per the Schedule of Events and Assessments ([Table 2](#)).

6.8.4 Retrospective 3-months Headache History

Retrospective 3-months headache history will be collected at Screening to record the first onset of migraine headache diagnosis, including the duration, frequency and location of the experienced migraine. Furthermore, if potential triggers such as food, medication, and symptoms associated with the migraine attack are known, these will be documented.

6.8.5 Physical and Neurological Examinations

The physical examination conducted at Screening will include assessments of all body systems other than genitourinary and at visits designated on the Schedule of Events and Assessments ([Table 2](#)). Measurement of height, and weight will be performed to monitor for signs of growth retardation. A special assessment will be made regarding the occurrence of decreased sweating and an elevation in body temperature above normal. Any findings during screening will be recorded as medical history, and any clinically significant abnormal findings during treatment will be recorded as an AE. At the EOS physical examination, only changes from baseline (Screening visit) will be noted.

Routine neurological exam at Screening will be aimed at detecting any possible causes of headache other than migraine. After the initiation of treatment, a neurological evaluation will help to assess for effects of SPN-538 on the nervous system, such as

impaired reflexes, balance problems, muscle weakness, paresthesia/numbness and tingling, speech difficulties, mental confusion or excessive fatigue. As part of the visual neurological examination, the following will be assessed at Visits 1 and 9: extraocular movements, pupils and confrontation visual fields for each eye ([Appendix 10.7](#)).

Equipment necessary for this part of the examination listed in the next section under Eye Exam.

6.8.6 Eye Exam

An eye examination (does not include intraocular pressure) will be performed at Visits 3, 6 and 9 (EOS). It will measure visual acuity and visualize the optic disc through a fundoscopic exam ([Appendix 10.8](#)). Subjects will be monitored for visual/ocular disturbances and potential signs of angle closure glaucoma during the participation in the study. If signs or symptoms of angle closure glaucoma (see below) develop and are observed during the clinical visits or reported at the intervening phone calls, subjects will be instructed to stop the SM immediately and be referred to an ophthalmologist or optometrist for priority exams (see below) as needed. If the subject goes to the ED, an exam by an ophthalmologist (preferred) or optometrist should be performed within 24 hours of the presentation.

Equipment at the site necessary to perform the visual neurological and eye exam consists of the following:

- Near card
- Wall Snellen Chart (optional, at Investigator's discretion based on outcome from routine eye exam)
- Penlight
- Hand held Ophthalmoscope (direct or Panoptic)
- Amsler grid (optional, at Investigator's discretion based on outcome from routine eye exam)

The Wall Snellen Chart uses a geometric scale to measure visual acuity, with normal vision at a distance being set at 20/20. The numerator represents the distance that the patient is standing from the chart (in feet), while the denominator represents the distance from which a person with perfect eyesight is still able to read the smallest line that the patient can clearly visualize.

The Amsler grid could be used to help detect early signs of retinal disease and monitor changes in vision after diagnosis.

Note: The Sponsor has appended Snellen chart ([Appendix 10.8.1](#)) and Amsler grid ([Appendix 10.8.2](#)) for every participating site as a tool to be used by the investigator if further examination is deemed necessary after a routine eye exam outcome.

Symptoms and signs of Angle Closure Glaucoma that might develop within the first 2-3 weeks of starting the medication, consist of the following:

- Rapid onset of pain that is often severe (typically, both eyes are affected)
- Headache (may be different from usual migraine)
- Nausea and/or vomiting
- Blurred vision, worse at distance and better at near
- Cloudy vision
- Halos around lights
- Conjunctival injection (redness)
- Mid-dilated and fixed or poorly reactive pupils

If symptomatic, the Sponsor recommends an urgent referral to an ophthalmologist or optometrist for priority exams (marked with asterisk):

- Best corrected visual acuity at far distance, usual correction at near distance*
- Pupil exam (Equal? Reaction to light? Afferent pupillary defect?) *
- Eye movements (up, down, horizontal) *
- Slit lamp exam (for corneal edema and narrow angle) *
- Intraocular pressure (applanation, air puff or Tonopen) *
- Anterior segment ocular coherence tomography (OCT) to confirm angle closure*
- Gonioscopy if intraocular pressure is elevated
- Dilated fundus exam (if possible) or B-scan ultrasound (for choroidal effusions)

6.8.7 Cognitive Assessment

Cognition refers to the mental processes involved in gaining knowledge and comprehension such as thinking, knowing, remembering, judging, and problem solving. These higher-level functions of the brain encompass language, imagination, perception, and the planning and execution of complex behaviors. Monitoring for cognitive/neuropsychiatric effects is recommended as part of standard clinical practice in TPM use ("[National Institutes of Health-DailyMed- Trokendi XR- Prescribing Information.](#)" 2022). The sponsor created a checklist ([Appendix 10.5](#)) of questions related to the subject's daily activities; subjects are asked to rate each question on a scale from 0 to 3 where 0 means never and 3 very often based on his/her recollection of the past weeks since the last visit. It is recommended to conduct the assessment with the parent(s) first. If discrepancies are found between different sources of information, the study staff will have to use their best clinical judgement.

Changes in cognitive function will be assessed at Visit 3, Visits 5 through 9 and at the safety follow-up phone call after the EOS.

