Topiramate (TPM), an antiepileptic drug (AED), is the only drug indicated for migraine prophylaxis in the pediatric patient population, specifically for children and adolescents ≥ 12 years of age. The efficacy and safety of TPM in migraine prophylaxis have been clearly demonstrated in several randomized, double-blind, placebo-controlled trials in thousands of patients (Jackson et al., 2015). These studies have provided consistent evidence that TPM reduces migraine frequency and acute medication use, improves quality of life, and reduces disability in patients with episodic and in those with chronic migraine, with or without medication overuse headache. As a result, TPM has become the most commonly prescribed migraine preventative in adults and is frequently recommended for migraine prophylaxis in children and adolescents (Kacperski et al., 2016; Silberstein, 2017).

Trokendi XR® (SPN-538) was developed by Supernus Pharmaceuticals as an extended release (XR) formulation of topiramate (TPM XR), a once a day (QD) product designed to be equivalent to TPM immediate release (IR) (Topamax®, Janssen Pharmaceuticals, Inc.) administered twice daily. Currently, Trokendi XR is marketed as an AED (monotherapy and adjunctive therapy) for patients 6 years of age and older and as a preventive for migraine headaches in adults and adolescents 12 years of age and older ("[National Institutes of Health-DailyMed- Trokendi XR- Prescribing Information.](#)," 2022). United States (US) Food and Drug Administration (FDA) approval of Trokendi XR was based on the product's demonstrated bioequivalence to Topamax.

The safety and tolerability of TPM has been studied extensively in adult and pediatric patients with epilepsy but has not been definitively established for prophylaxis of migraine headache in patients younger than 12 years of age. In a meta-analysis of randomized clinical trials of TPM in children with migraine <18 years of age, the most frequently reported adverse events (AEs) included paresthesia, upper respiratory tract infections, fatigue, weight decrease, anorexia, and cognitive impairments ([Le, Yu, Wang, Ali, & Guo, 2017](#)). Most AEs, including those leading to discontinuation of TPM, occurred during the titration period and did not worsen during maintenance ([Lainez et al., 2007](#)). In pediatric patients, slow dose titration is recommended to alleviate AEs, and dose reductions may improve treatment compliance.

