In previous migraine studies MIGR-001 ([Silberstein, Neto, Schmitt, Jacobs, & Group, 2004](#)), MIGR-002 ([Brandes et al., 2004](#)), MIGR-003 ([Diener et al., 2004](#)), and MIG-3006 ([Lewis et al., 2009](#)), most AEs reported with the use of TPM were mild to moderate in severity, and no unusual or unexpected safety risks were identified. However, long-term TPM treatment requires continuous assessment for AEs that are specifically attributable to this drug. These include ophthalmologic side effects (acute myopia, secondary angle closure glaucoma, and visual field defects), oligohydrosis and hyperthermia, treatment-related laboratory abnormalities (e.g., metabolic acidosis, hyperammonemia, and changes in complete blood count values), nephrolithiasis, negative effects on growth, and suicidal behavior and ideation.

Monitoring for neuropsychiatric effects and cognitive impairment is of crucial importance because of the effect of TPM on cognitive function, specifically on concentration/attention, memory, and speech/language abilities. This risk for cognitive adverse reactions is dose dependent and is greater in younger pediatric patients (6 to 11 years) than in older children (12 to 17 years) ("[National Institutes of Health-DailyMed- Trokendi XR- Prescribing Information.](#)," 2022; "[National Institutes of Health-DailyMed- Topamax- Prescribing Information.](#)" 2022).

Trokendi XR is an approved agent for the prophylaxis of migraine in adults and adolescents 12 years of age and older; however, its efficacy as a migraine preventative has not been established in the 6-to-11 year age range. In this study (538P401), the efficacy and safety of Trokendi XR as a preventative therapy for migraines in this younger pediatric population will be explored. The XR formulation of SPN-538 is expected to be beneficial in this patient population where, compared to the IR TPM products, it offers more constant plasma drug concentrations, less frequent dosing, and an improved AE profile ([Silberstein, 2017](#)).

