2.6 Secondary Endpoints

The secondary efficacy endpoints are:

1. Responder, defined as a subject with $\geq 50\%$ reduction in the MMDs during the last 4 weeks of the Treatment Phase relative to Prospective Baseline Period.

2. Change from baseline in the monthly migraine-specific acute rescue medication use in the last 4 weeks of the Treatment Phase.
3. Change in the monthly rate of total headache days (migraine and non-migraine), duration and severity.
4. Change in the time to onset of action, defined as the time to first statistically significant treatment effect observed and maintained until the EOS.
5. Change from baseline in the Headache Disability Score as measured by PedMIDAS during the last 4 weeks of the Treatment Phase.
6. Change from baseline in the HRQoL as measured by the PedsQL 4.0 Total Scale Score during the last 4 weeks of the Treatment Phase for the self-report and the parent-report.

The safety endpoints are:

1. Incidence of AEs.
2. Clinical laboratory test results (blood chemistry and hematology, urinalysis).
3. Vital signs, physical and neurological examinations, and ECGs.
4. C-SSRS assessment.
5. Cognitive Assessment.

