5.1.3 Visit 3 (+2 days) – Randomization (Day 1)

The following assessments will be conducted at this visit:

- Review inclusion/exclusion criteria
- Record vital signs (pulse rate, BP, temperature, and RR)
- Collect urine sample for pregnancy test (FOCP only)
- Administer C-SSRS
- Review and record concomitant medications
- Review Headache Diary for eligibility
- Administer PedMIDAS, PedsQL 4.0 scales
- Perform cognitive assessment
- Perform eye exam
- Record AEs
- Randomization
- Dispense SM (4-week supply) and provide instructions for dose titration

5.1.4 Titration Period (Days 1 to 56, Week 1 to end of Week 8)

Intervening Phone Calls

At Days 14 (± 2 days) and 43 (± 2 days) there will be telephone calls to subjects to assess the tolerability of the SM treatment.

The following assessments will be made during these telephone contacts:

- Review and record concomitant medications
- Record AEs
- Provide guidance (as needed) on dose reduction

Visit 4 (Day 29 \pm 7 days)

During Treatment Phase (Visits 4 through 9), sample collection and testing have been specified for respective visits by the Sponsor. Besides the testing specified during these respective visits, repeat testing for clinical laboratory parameters, vital signs, and/or ECG may be permitted, at the discretion of the Investigator. However, these repeat testing will require justification from the site and agreement with the Medical Monitor and the Sponsor on a case-by-case basis prior to conducting the tests.

The following assessments will be conducted at this visit:

- Perform physical examination (excluding genitourinary system) including height and weight, and neurological examination

- Record vital signs (pulse rate, BP, temperature, and RR)
- Collect urine sample for pregnancy test (FOCP only)
- Administer C-SSRS
- Review and record concomitant medications
- Review Headache Diary
- Record AEs
- Collect SM and assess adherence; retrain as needed
- Dispense SM (4-week supply) and review medication instructions with subject and caregiver
- Placebo training refresher

5.1.5 Maintenance Period (Days 57 to 140, Week 9 to the end of Week 20)

Visit 5 (Day 57 ± 7 days)

The following assessments will be conducted at this visit:

- Perform 12-lead ECG
- Record vital signs (pulse rate, BP, temperature, and RR)
- Collect blood samples for hematology and serum chemistry
- Collect urine sample for urinalysis and for pregnancy test (FOCP only)
- Collect urine sample for drug screen

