- Administer C-SSRS
- Review and record concomitant medications
- Review Headache Diary
- Administer PedMIDAS, PedsQL 4.0 scales
- Perform cognitive assessment
- Record AEs
- Collect SM and assess adherence; retrain as needed
- Dispense SM (4-week supply) and review medication instructions with subject and caregiver

Visits 6 (Day 85 ± 7 days) and Visit 7 (Day 113 ± 7 days)

The following assessments will be conducted at these visits:

- Perform physical examination (excluding genitourinary system) including height and weight, and neurological examination
- Record vital signs (pulse rate, BP, temperature, and RR)
- Collect urine sample for pregnancy testing (FOCP only)
- Collect urine sample for drug screen
- Perform eye exam (only at Visit 6)
- Administer C-SSRS
- Perform cognitive assessment

- Review and record concomitant medications
- Review Headache Diary
- Record AEs
- Collect SM and assess adherence; retrain as needed
- Dispense SM (4-week supply) and review medication instructions with subject and caregiver
- Placebo training refresher (only at Visit 6)

Intervening Phone Calls

At Days 71 (± 2 days), 99 (± 2 days) and 127 (± 2 days), there will be telephone calls to subjects to assess the tolerability of SM treatment.

The following assessments will be made during these telephone contacts:

- Review and record concomitant medications
- Record AEs
- Provide guidance (as needed) on dose reduction, up to one dose reduction will be allowed for safety and tolerability during this period. Additional dose titration related to body weight changes will be reviewed and approved by the Medical Monitor and the Sponsor on a case by case basis.

5.1.6 Taper Period (Days 141 to 161, Week 21 to the end of Week 23)

Intervening Phone Call

At Day 148 (± 2 days) there will be a telephone call to subjects to assess the tolerability of the SM treatment.

The following assessments will be made during these telephone contacts:

- Review and record concomitant medications
- Record AEs
- Provide guidance (as needed) on dose reduction

Visit 8 (Day 141 \pm 7 days)

The following assessments will be conducted at this visit:

- Perform physical examination (excluding genitourinary system) including height and weight, and neurological examination
- Record vital signs (pulse rate, BP, temperature, and RR)
- Collect blood samples for hematology and serum chemistry
- 
- Collect urine sample for urinalysis and for pregnancy testing (FOCP only)

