10.5 Cognitive Assessment

Subject I.D. _____

Visit Date _____

Cognitive Assessment

This assessment is administered by asking the child questions related to his/her daily activities in the past weeks since the last visit.

To obtain accurate information, we suggest conducting the assessment with the parent(s) first. If discrepancies are found between different sources of information, the study staff will have to use his/her best clinical judgement.

Since your last visit to the study doctor, please answer the following questions:

On a scale from 0 to 3, where 0= never, 1= sometimes (once or twice a week), 2=often (more than 3 times a week), 3= very often (every day)

N.	Question	Answer
1.	Do you have trouble remembering things that your mom, teacher or friends have said to you?	
2.	Do you have trouble recognizing objects and remembering how they look?	
3.	Do you feel that you sometimes don't know what to do especially at school?	
4.	Do you have trouble answering questions or find it difficult to respond to questions?	
5.	Do you feel unusually tired or sleepy?	
6.	Do you feel that your activity has recently slowed down?	
7.	Do you have trouble paying attention and concentrating: a. at school? b. at home while doing your homework? c. when playing with your friends?	

Ver. 1.0

Date 25 June 2019

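### For children who attend Visit 4 and stay in the study, no cognitive checklist score covers Weeks 1-4 of treatment, so the summary of safety endpoint 5 is silent on that period

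*Protocol*

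**What the plan says.** Cognitive assessment is the fifth safety endpoint in Protocol Section 2.6 ("5. Cognitive Assessment") and in SAP Section 5.3. It is measured with a short sponsor-written checklist (Appendix 10.5), scored 0 to 3 per question.

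On timing, Section 6.8.7 states: "Changes in cognitive function will be assessed at Visit 3, Visits 5 through 9 and at the safety follow-up phone call after the EOS". Table 2 has no mark at Visit 4, the Visit 4 procedure list in Section 5.1.4 does not include the checklist, and the SAP schedule also leaves Visit 4 blank. At Visit 5 the procedure list in Section 5.1.5 has it ("Perform cognitive assessment").

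On recall, Section 6.8.7 says that the child answers "based on his/her recollection of the past weeks since the last visit". The form opens with: "Since your last visit to the study doctor, please answer the following questions".

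On analysis, Protocol Section 7.11 and SAP Section 9.7 list the responses and summarize them by visit and arm. SAP Section 9 rules out inferential tests on safety data.

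**The concern.** Skipping a visit would do no harm if the next form looked back to the previous form. This one looks back to the previous visit, and Visit 4 is a clinic visit at which the form is not given. The Visit 3 form looks back over time before the first dose, and the Visit 5 form looks back to Visit 4. The interval between Visits 3 and 4 falls between them.

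The interval matters on the protocol's own account. The Introduction says "Monitoring for neuropsychiatric effects and cognitive impairment is of crucial importance because of the effect of TPM on cognitive function", and adds that the risk depends on dose and is greater at ages 6 to 11 than in older children. It also reports that "Most AEs, including those leading to discontinuation of TPM, occurred during the titration period and did not worsen during maintenance". Section 3.2.2 describes topiramate adverse events as often transient. The start of treatment and the first planned dose step both fall in Weeks 1-4. A child whose attention or memory suffers in that period and recovers before Visit 4 could truthfully score 0 on every later form.

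**Working it through.** The plan gives no figure for checklist coverage, so there is none to reproduce. The check is a day count.

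**Inputs** (Protocol Table 2 and Sections 4.2, 5.1.3 to 5.1.6)
- First dose: Visit 3, Day 1.
- Nominal clinic visits: Visit 4 Day 29, Visit 5 Day 57, Visit 6 Day 85, Visit 7 Day 113, Visit 8 Day 141.
- Titration: Days 1-56. Treatment Phase: Days 1-140.
- Visit 4 window: ±7 days, so Day 22 to Day 36.
- Checklist during treatment: Visits 5, 6, 7 and 8.

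**Rule.** A checklist at visit *k* covers the days from visit *k*−1 up to the day before visit *k*.

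**Coverage at nominal days**
- Visit 5 form: Days 29-56
- Visit 6 form: Days 57-84
- Visit 7 form: Days 85-112
- Visit 8 form: Days 113-140
- No form: Days 1-28

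**Size of the gap** = (day of Visit 4) − 1
- Visit 4 on Day 22: 21 days; 21/140 = 15% of treatment, 21/56 = 37.5% of titration.
- Visit 4 on Day 29: 28 days; 28/140 = 20%, 28/56 = 50%.
- Visit 4 on Day 36: 35 days; 35/140 = 25%, 35/56 = 62.5%.

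**Exception.** Under Protocol Sections 3.4.1 and 3.4.2 a child who stops early completes the Visit 9 procedures, which include the checklist. If that child never attended Visit 4, the recall reaches back to Visit 3. The only checklist data on Weeks 1-4 therefore come from children who leave before Visit 4, a selected group.

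**After either change under the fix**, uncovered treatment days fall from 28 to 0 at nominal days.

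**The case against.** The strongest reply is that Weeks 1-4 are monitored by other means. Cognitive and memory impairment is an adverse event of special interest, reportable within 24 hours (Protocol Section 6.6.9). Adverse events are actively sought at every contact after the first dose (Section 6.6.2), which includes the Day 14 call and Visit 4. The Visit 4 neurological examination looks for confusion, speech problems and fatigue, which partly overlap the checklist. Events of special interest are summarized by arm (SAP Section 9.1). All of this stands. A reader might infer from the schedule that early cognitive effects go unobserved, and the documents do not support that. These sources do not, however, produce checklist scores.

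A second reply is that the loss is narrow. Only symptoms that begin and fully resolve before Visit 4 are missed, since anything that persists falls within the Visit 5 recall. The Introduction places most adverse events in titration as a whole, not in its first half, and Weeks 5-8 are covered. The risk is described as dose dependent, and later increments come after Day 28. This stands in the main, with one limit: the second planned step, 50 mg/day from Week 3, is 50/20 = 2.5 mg/kg at the minimum entry weight of 20 kg and 50/25 = 2.0 mg/kg at 25 kg. The lightest children can thus be in the stated target range of 2 to 3 mg/kg/day inside the gap.

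Third, the schedule is stated consistently and its visit list was revised in Version 4.0, so it looks deliberate. That is fair: this is a design choice, not a contradiction. But no rationale is given for leaving Weeks 1-4 without a score.

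Finally, a site might take the last visit to mean the last visit with a checklist. The form does not say so, and mixed readings across about 35 planned sites would make Visit 5 scores hard to compare.

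**Conclusion.** The point holds for children who attend Visit 4 and continue: no checklist score covers Days 1-28 (21 to 35 days with the visit window). It rests on reading the form as written and on the nominal visit schedule.

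Two stronger readings should be avoided. One is that no child ever supplies checklist data on Weeks 1-4; those who stop before Visit 4 should do so at the termination visit. The other is that the endpoint is biased by a known amount in favour of SPN-538. If topiramate causes early transient effects, more of them would be expected on SPN-538, but the documents give no rate for effects that resolve before Visit 4. The 20% and 50% figures measure calendar time, not missed events. A by-visit table without a Visit 4 row is silent on Weeks 1-4; it does not report a wrong value for them.

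The endpoint is descriptive, and no hypothesis test depends on it. This is a cheap improvement of low to moderate priority.

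**What to change.** Either change closes the gap.

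1. Give the existing Appendix 10.5 checklist at Visit 4, and align Table 2, Sections 5.1.4 and 6.8.7 and the SAP schedule. The cost is a few minutes at a visit that already takes place. This is preferable because recall stays at about 4 weeks.
2. Keep the schedule and change the opening of the form, and the matching sentence in Section 6.8.7, so that recall runs from the last time these questions were asked. Visit 5 then covers Days 1-56. The cost is an 8-week recall for a child aged 6 to 11. Because the scale is anchored to frequency per week, symptoms confined to the first weeks may also be diluted over the longer period.

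Children already past these visits will not have the new data. Option 1 would leave a partly filled Visit 4 row, and option 2 would mix two recall periods at Visit 5. The summary should say which children were assessed under which rule. If neither change is made, the report should state that the checklist summary does not cover Weeks 1-4 and refer the reader to the adverse event data for that period.
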